1.0 Background

Hypertension (HTN) is more common and more harmful for African Americans than for any other ethnic group (AHA, 2020a). More than half of African American adults, about 15 million people, have HTN (AHA, 2017; Annie E. Casey Fdn, 2019). Furthermore, African Americans are 4 times less likely to adhere to HTN meds compared to their white counterparts (Schoenthaler et al. 2016). Tailored approaches to reduce the racial gap in HTN morbidity and mortality, particularly those supporting med adherence, are needed in primary care (NHLBI, 2020). Importantly, HTN is one of most common co-morbidities in Covid19 hospitalizations, particularly for African Americans (CDC 2020). Moreover, media coverage of a possible link between certain HTN meds, called RAAS inhibitors, and severe Covid19 outcomes may have alarmed HTN patients about the safety of their meds. As a result, the ACC (March, 2020) issued guidelines recommending all patients adhere to HTN meds during the pandemic unless advised by their physicians, as there is no evidence of a link between HTN drugs and Covid19 severity. In fact, severe heart complications have been reported among Covid19 patients that stopped HTN meds, including RAAS inhibitors, could worsen outcomes (ACC, July 2020). Thus, in the time of Covid19, supporting med adherence of African Americans with HTN is extremely urgent.

2.0 Goals

We propose a digital adherence solution to help reduce HTN-related disparities among African Americans, called Memento.HTN, which is innovative in three key ways: 1) it is the first-ever linked digital provider platform and patient SMS text system for HTN medication adherence; 2) it is culturally-tailored for African Americans with HTN; and 3) it has unique monitoring functionality allowing providers to monitor individual patient adherence, support 'new start' patients, who are at increased risk for non-adherence, and to track group adherence rates by drug class, pill format, and patient demographics in order to inform clinical therapeutics. Requiring only minutes of staff or prescriber monitoring per day, the Memento system simplifies and facilitates provider delivery of adherence support. The provider platform sends patients interactive SMS pill reminders plus culturally-sensitive motivational, educational, spiritual/stress-supportive, and customizable texts, along with texts that target intentional non-adherence. Importantly, Memento allows 2-way communication between providers and patients, and automatically alerts providers when a patient is having clinically-significant pill lapses.

Specific Aim 1: Develop an individually-tailored, culturally-sensitive digital health intervention comprised of a provider platform and linked patient SMS system to promote medication adherence in African Americans with HTN.

Specific Aim 2: Implement a 6-wk pilot to evaluate feasibility and short-term effectiveness for improving adherence.

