3.0 Inclusion/Exclusion Criteria

A detailed description of how subjects will be consented, study procedures, materials and potential risks for the study is provided below:

Inclusion/Exclusion Criteria for Patient usability and formative testing focus groups or individual interviews:

Inclusion: African American adults, age 18 and older, diagnosed with hypertension/high blood pressure, prescribed HTN meds, own a cellphone (basic or smart). Exclusion: Undergoing cancer treatment; pregnancy; end stage renal disease.

Inclusion/Exclusion Criteria for Patient 6 week pre-post evaluation: Inclusion: African American adults, age 18 and older, diagnosed with hypertension/high blood pressure, prescribed HTN meds, own a cellphone (basic or smart). Exclusion: Participation in other clinical research; undergoing cancer treatment; pregnancy; end stage renal disease.

Inclusion/Exclusion Criteria for Clinician usability and formative testing focus groups: Inclusion: Licensed clinicians (MD, PA, NP, RN, PharmD et al.) who work in primary care settings and prescribe anti-hypertensive medication treatment to adult patients with primary hypertension. Exclusion: Participation in other health services research.

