Focus groups (or interviews) with Patients and Focus Groups (or interviews) with Healthcare Providers: All participants in focus groups will complete the consent process via Qualtrics online platform. The consent statement will emphasize that participation will not in any way affect the services he/she receives from any provider or agency. The potential participant will read that participation is voluntary and that the potential participant may

Protocol #: NIH 1R43MD009454-01A1

Version: 2

April 11, 2021

terminate participation at any time and may skip any questions that he or she does not wish to answer. Individuals, who are comfortable proceeding, will provide a signature online in the Qualtrics form.

Patient 6 week Pre-post evaluation: All potential participants will review inclusion criteria and online consent form via Qualtrics. The consent form for patient participants in the 6-week evaluation of Memento will describe procedures and potential risks. It will emphasize that participation is voluntary and will not in any way affect employment or access to any services received from any provider or agency or clinic, and that participants can discontinue involvement at any time. Furthermore, as done in our other adherence studies, the consent will state the possibility that SMS texts or the linked provider platform may malfunction during the evaluation, and that participants should continue to use whatever other methods they normally use to remember their pills for the duration of the study. It will also state that any information offered as a part of the study should not replace a participant's own physician's advice. It will also state that the study involves potential privacy loss and breach of confidentiality. After the informed consent is electronically signed, the study will proceed. At the completion of the 6-week period, participants will participate in a focus groups with up to 10 others or individual interviews (via zoom/phone) to gain their feedback on their experience with of the Memento program.

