9.0. Outcome Measures

HTN med adherence will be assessed by the Adherence to Refills and Medication Scale (ARMS), a well-validated self-report measure used widely in studies with minority patients and/or those with low literacy (Buis et al., 2019; Kripalani et al., 2009; McNaughton et al., 2014). We will also use Segeral et al. (2010) 3-item adherence measure, as in our prior research (Pagan-Ortiz et al., 2019). Validated self-report measures correlate with clinical outcomes and are desirable to use in research with African American patients, who may resist providing bio-specimens due to historical mistrust (Ewing et al., 2019, Stirratt et al., 2015). Lastly, electronic pill bottles are cumbersome, expensive, and often ineffective for promoting and tracking adherence (Choudhry et al., 2017; Volpp et al., 2017).

Secondary: Adherence self-efficacy will be assessed with the HTN med adherence self-efficacy scale (MASES) (Ogedegbe et al. 2003). HTN knowledge will be assessed using the NHLBI HTN Knowledge Scale (Carter-Edwards et al., 2002). Stress burden will be assessed using Perceived Stress Scale (Cohen et al., 1983). **Exploratory:** BP will be measured at baseline and 6 weeks. **Primary Hypothesis:** Participants will show greater HTN med adherence at 6 wks compared to baseline.

Secondary Hypothesis: Participants will show greater HTN adherence self-efficacy, greater HTN knowledge, and lower stress burden at 6 wks compared to baseline. **Exploratory Hypothesis:** Participants will show a decrease in systolic BP at 6 wks compared to baseline. **Data analyses:** We will conduct one-tailed paired t-tests at the .05 level for primary and exploratory hypotheses and McNemar's chi square for secondary hypotheses. Data from our Phase 1 evaluation of short-term effectiveness will be used to determine the sample size necessary for an adequately-powered Phase 2 RCT.

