10.0 Statistical Considerations

Because this is a feasibility study, the pre-post evaluation sample size is not based on power calculations. In Phase 2, a sample size will be created with a power of at least 90% with a two-sided alpha level of .05.

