### **Analysis plan:**

**Measures: Primary:** HTN med adherence will be assessed by the Adherence to Refills and Medication Scale (ARMS), a well-validated self-report measure used widely in studies with minority patients and/or those with low literacy (Buis et al., 2019; Kripalani et al., 2009; McNaughton et al., 2014). We will also use Segeral et al. (2010) 3-item adherence measure, as in our prior research (Pagan-Ortiz et al., 2019). (NB: The team revised the adherence measure approach to use a single measure, namely the Wilson et al. (2016) Self-Report Medication Adherence scale.) **Secondary:** Adherence self-efficacy will be assessed with the HTN med adherence self-efficacy scale (MASES) new (Ogedegbe et al. 2003). Stress burden will be assessed using Perceived Stress Scale (Cohen et al., 1983). HTN knowledge will be assessed using the NHLBI HTN Knowledge Scale (Carter-Edwards et al., 2002). **Primary Hypothesis:** Participants will show greater HTN med adherence at 6 wks compared to baseline. **Secondary Hypothesis:** Participants will show greater HTN adherence self-efficacy, greater HTN knowledge, and lower stress burden at 6 wks compared to baseline.

**Data analyses:** We will conduct one-tailed paired t-tests at the .05 level for primary hypotheses. Data from our Phase 1 evaluation of short-term effectiveness will be used to determine the sample size necessary for an adequately-powered Phase 2 RCT.

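### The plan calls a single-arm 6-week change in self-reported adherence short-term effectiveness, but without a comparator it can only estimate change from baseline

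*Protocol*

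**What the plan says.** Specific Aim 2 in Protocol 2.0 is to "Implement a 6-wk pilot to evaluate feasibility and short-term effectiveness for improving adherence". The SAP carries the label forward: "Data from our Phase 1 evaluation of short-term effectiveness will be used to determine the sample size necessary for an adequately-powered Phase 2 RCT". Protocol 9.0 contains the same sentence.

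The study behind the label has one group. Protocol 3.0 introduces it under "Inclusion/Exclusion Criteria for Patient 6 week pre-post evaluation", and no control group, external benchmark, run-in or repeated baseline is described anywhere. The primary hypothesis is "Participants will show greater HTN med adherence at 6 wks compared to baseline". The SAP test is "We will conduct one-tailed paired t-tests at the .05 level for primary hypotheses"; the Protocol has "We will conduct one-tailed paired t-tests at the .05 level for primary and exploratory hypotheses".

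The adherence measures named in Protocol 9.0 and the single scale that replaces them in the SAP are all self-report. On size, Protocol 10.0 says only "Because this is a feasibility study, the pre-post evaluation sample size is not based on power calculations". Neither document limits how a significant result may be interpreted.

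**The concern.** The hypothesis and the stated aim ask different questions. The hypothesis asks whether adherence is higher at 6 weeks than at baseline, and the paired t-test answers that. Effectiveness asks whether adherence is higher than it would have been without Memento, and nothing in the design estimates that second quantity.

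The plan itself supplies other reasons why scores might move:

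- Participants know they are receiving the texts, rate their own adherence, and retake the same assessments at 6 weeks (Protocol 5.0, 9.0).
- Each participant is given a new home blood pressure cuff at the start (Protocol 5.0). Having one may affect pill-taking whether or not any texts are sent.
- People prescribed antihypertensives within the last 8 weeks are included (Protocol 5.0). Their adherence may be changing anyway.

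Two things are at stake: what the report may conclude, and what is carried into Phase 2. Sizing the RCT is the one use of the result that the documents state.

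**Working it through.** **Inputs from the documents.** Paired t-test, one-tailed, level 0.05 (Protocol 9.0; SAP). One group, two time points (Protocol 3.0, 5.0). Phase 2 to have at least 90% power at two-sided 0.05 (Protocol 10.0). The documents give no sample size, SD, effect size or dropout rate for the pre-post study, so there is no figure of the plan's own to reproduce.

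**Assumed inputs.** n = 20, 30 or 50. Memento has zero effect, but mean adherence improves by d for other reasons, where d is in SDs of the within-person change: 0, 0.1, 0.2 or 0.3.

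**Step 1: how often the planned test is significant when Memento does nothing.** The null of the paired test is zero mean change. Under a shift d, the statistic follows a noncentral t with n − 1 degrees of freedom and noncentrality d√n, so

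P(significant) = 1 − F(t₀.₉₅,ₙ₋₁; n − 1, d√n).

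Example: n = 20, d = 0.3. The noncentrality is 0.3 × √20 = 1.342, the critical value is 1.729, and the probability is 0.363.

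| Shift d | n = 20 | n = 30 | n = 50 |
|---|---|---|---|
| 0 | 0.050 | 0.050 | 0.050 |
| 0.1 | 0.112 | 0.134 | 0.172 |
| 0.2 | 0.217 | 0.283 | 0.401 |
| 0.3 | 0.363 | 0.484 | 0.673 |

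The 5% level holds against no change. It does not hold against no effect of Memento unless the drift is zero.

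**Step 2: is one-sidedness the cause?** With a two-sided 0.05 test, the probability of a significant improvement at d = 0.3 is 0.246, 0.355 and 0.548 for n = 20, 30 and 50. These are lower, but still far above the nominal 0.025 in that tail. The cause is the missing comparator.

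**Step 3: what a comparator would do.** Two arms sharing the same 0.3 SD shift, with no treatment effect, were compared by a one-tailed two-sample t-test on change scores (40,000 simulated trials each). The rejection rate was 0.0495, 0.0497 and 0.0496 at total n = 20, 30 and 50. The shared drift cancels.

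**Step 4: consequence for Phase 2 if the raw change were used as the between-arm effect.** For a comparison of mean changes, n per arm = 2(1.960 + 1.282)² / δ², with δ in SDs of the change score. Suppose the pilot shows a change of 0.5 SD, of which 0.2 SD is non-specific (both assumed).

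- δ = 0.5: 2 × 10.507 / 0.25 = 84.1, so 85 per arm.
- δ = 0.5 − 0.2 = 0.3: 2 × 10.507 / 0.09 = 233.5, so 234 per arm.

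A trial of 85 per arm facing a true effect of 0.3 SD would have power of about Φ(0.3 × √(85/2) − 1.960) = Φ(−0.004), or 50%, against the 90% intended.

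**The case against.** The strongest reply is that the documents already frame the study modestly. It is called a pre-post evaluation throughout, Protocol 10.0 calls it a feasibility study, the hypotheses claim only change from baseline, and the randomised comparison is left to Phase 2. This stands, and it confines the point to wording and interpretation: a single-arm pilot is a reasonable design here. It does not remove the point, because Aim 2, Protocol 9.0 and the SAP all use the stronger word and nothing qualifies it.

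The percentages also rest on assumed sample sizes and drifts. That stands too. They show how the test behaves and do not measure this trial's error rate.

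A reader might infer several stronger things that the documents do not support:

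- **That the trial will declare Memento effective at p < .05.** There is no success criterion, go/no-go threshold or reporting rule to that effect.
- **That the one-tailed test is the fault.** Step 2 shows that a two-sided test has the same defect.
- **That regression to the mean inflates the result.** Eligibility in Protocol 3.0 has no low-adherence threshold, so selection gives little reason to expect it.
- **That participants' own reminder methods bias the change.** The consent text says "participants should continue to use whatever other methods they normally use to remember their pills". A practice that continues unchanged does not create a difference between baseline and week 6.
- **That staff contact after missed pills is contamination.** Protocol 2.0 makes lapse alerts and two-way communication features of Memento, so improvement from outreach may be part of its effect.
- **That all drift favours the hypothesis.** The documents do not establish the direction. Socially desirable answering could inflate baseline scores as well.
- **That the plan will use the raw change as the Phase 2 effect.** The documents say pilot data will determine the sample size, but not which quantity will be used.

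**Conclusion.** The point holds as a mismatch between the stated aim and what the design can show, and the wording should be changed. A significant paired t-test, one- or two-sided, will support a statement about change from baseline in self-reported adherence. It will not support a statement that Memento is effective.

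That conclusion rests on the design alone. Its size is illustrative: 11% to 67% significant results under no Memento effect, for an assumed non-specific improvement of 0.1 to 0.3 SD and an assumed n of 20 to 50. The Phase 2 figures, 85 against 234 per arm, are likewise conditional on the assumed 0.5 SD change and 0.2 SD non-specific share. They show why the plan should say which pilot quantities will be used.

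**What to change.** 1. In Protocol 2.0 (Specific Aim 2), Protocol 9.0 and the SAP, replace the effectiveness wording with: *feasibility and preliminary within-participant change in self-reported adherence over 6 weeks*.
2. In Protocol 9.0 and the SAP, make the mean change with its confidence interval the main result.
3. Add one sentence to both: *Without a concurrent comparator, the test concerns change from baseline and will not be reported as evidence that Memento is effective; that question is left to the Phase 2 RCT.*
4. Where both documents say the pilot will inform the Phase 2 sample size, add that the raw pre-post change will not be used as the between-arm effect. Pilot data would inform the SD, the correlation between time points, retention and feasibility.

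This needs no new data, participants or study arm. The downside is a less favourable headline claim, and the Phase 2 effect size will need another justification.

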3.0 Inclusion/Exclusion Criteria

A detailed description of how subjects will be consented, study procedures, materials and potential risks for the study is provided below:

Inclusion/Exclusion Criteria for Patient usability and formative testing focus groups or individual interviews:

Inclusion: African American adults, age 18 and older, diagnosed with hypertension/high blood pressure, prescribed HTN meds, own a cellphone (basic or smart). Exclusion: Undergoing cancer treatment; pregnancy; end stage renal disease.

Inclusion/Exclusion Criteria for Patient 6 week pre-post evaluation: Inclusion: African American adults, age 18 and older, diagnosed with hypertension/high blood pressure, prescribed HTN meds, own a cellphone (basic or smart). Exclusion: Participation in other clinical research; undergoing cancer treatment; pregnancy; end stage renal disease.

Inclusion/Exclusion Criteria for Clinician usability and formative testing focus groups: Inclusion: Licensed clinicians (MD, PA, NP, RN, PharmD et al.) who work in primary care settings and prescribe anti-hypertensive medication treatment to adult patients with primary hypertension. Exclusion: Participation in other health services research.

4.0 Enrollment

Recruitment:

Patient recruitment usability and formative usability testing: Primary care recruitment resources include: UChicago Primary Care Group, Prisma Baptist Hospital, and Brigham & Women's Hospital, including affiliated clinics, and UserInterviews, an online recruitment source. Clinic ads and flyers will be posted on bulletin boards and other clinic-based outlets, and we will ask clinic staff to share flyers and study information with potential participants. Flyers & ads will state what the study is about, who is funding it, who might be eligible, what the length of time & compensation would be, and will provide contact number for more information about the study. Individuals who contact us will be screened (via zoom, phone or face-to-face) further for inclusion/exclusion criteria. Individuals who meet study criteria and agree to participate in the study will complete an online consent form in Qualtrics.

Patient Recruitment 6 week pre-post evaluation. Primary care recruitment resources include: UChicago Primary Care Group, Prisma Baptist Hospital, and Brigham & Women's Hospital, including affiliated clinics, and UserInterviews. Clinic ads and flyers will be posted on clinic bulletin boards and other clinic-based outlets, and we will ask clinic staff to share flyers and study information with potential participants. Individuals who contact us will be screened further via zoom or phone for inclusion/exclusion criteria. Individual who meet study criteria and agree to participate in the study will complete an online consent form in Qualtrics. Individuals who meet study criteria and sign the informed consent will complete online baseline assessments, including obtaining a BP reading using a BP cuff which we will donate to each person as a part of the study.

Healthcare provider usability and formative focus group participants. Healthcare providers will be recruited through signs and word of mouth in the University of Chicago Medicine, Prisma Hospital and Brigham & Women's Hospital, as well as through Boston-area community health centers where [name] has numerous contacts and/or through UserInterviews.

Consent Process:

The study will be conducted according to ethical principles stated in the Declaration of Helsinki (2013), ethics approval will be obtained before initiating study, consent forms will take into consideration the well-being, free-will and respect of the participants, including respect of privacy, etc. A detailed

Focus groups (or interviews) with Patients and Focus Groups (or interviews) with Healthcare Providers: All participants in focus groups will complete the consent process via Qualtrics online platform. The consent statement will emphasize that participation will not in any way affect the services he/she receives from any provider or agency. The potential participant will read that participation is voluntary and that the potential participant may

Protocol #: NIH 1R43MD009454-01A1

Version: 2

April 11, 2021

terminate participation at any time and may skip any questions that he or she does not wish to answer. Individuals, who are comfortable proceeding, will provide a signature online in the Qualtrics form.

Patient 6 week Pre-post evaluation: All potential participants will review inclusion criteria and online consent form via Qualtrics. The consent form for patient participants in the 6-week evaluation of Memento will describe procedures and potential risks. It will emphasize that participation is voluntary and will not in any way affect employment or access to any services received from any provider or agency or clinic, and that participants can discontinue involvement at any time. Furthermore, as done in our other adherence studies, the consent will state the possibility that SMS texts or the linked provider platform may malfunction during the evaluation, and that participants should continue to use whatever other methods they normally use to remember their pills for the duration of the study. It will also state that any information offered as a part of the study should not replace a participant's own physician's advice. It will also state that the study involves potential privacy loss and breach of confidentiality. After the informed consent is electronically signed, the study will proceed. At the completion of the 6-week period, participants will participate in a focus groups with up to 10 others or individual interviews (via zoom/phone) to gain their feedback on their experience with of the Memento program.

